1.2. BLU-5937 Pharmacology

BLU-5937, a small molecule of the imidazopyridine chemical class, is a potent, selective and non-competitive P2X3 homotrimeric receptor antagonist. P2X3 receptors are ATP ion-gated channels located on primary afferent neurons. ATP released from damaged or inflamed tissues in the airways acts on P2X3 receptors on primary afferent neurons, triggering depolarisation and action potentials that are transmitted centrally and interpreted as urge to cough. There are preclinical and clinical evidence supporting the role of P2X3 receptors in hypersensitization of the cough reflex, leading to chronic cough. By inhibiting P2X3 receptors on the primary sensory neurons, BLU-5937 would inhibit the hypersensitization of the cough reflex and, hence, the exaggerated cough experienced in chronic cough patients.

1.3. Clinical Indication

[figure not shown]
BLU-5937 is an investigational drug that is developed for the treatment of unexplained or refractory chronic cough.

1.4. Nonclinical Experience

1.5. Nonclinical Pharmacokinetics

[figure not shown]

Protocol Nº BUS-P2-01 Sponsor Project Nº CL-5937-02

1.7. Clinical Experience

Sponsor Project № CL-5937-02

1.8. Study Rationale

With extensive efforts in animals, one P2X3 antagonist drug has started to validate the mechanism of P2X3 inhibition in cough hypersensitivity in clinical trials, gefapixant (AF-219, MK-7264). In 2014, a proof-of-concept phase II study highlighted a large decrease in cough frequency (75%) with gefapixant 600 mg BID vs placebo in 24 chronic cough patients (Abdulqawi, 2015). Follow-up studies exploring a wide range of doses have indicated a clear dose-response relationship between potent cough suppression and gefapixant administration, indicating promising potential for the P2X3 antagonist in being the first new cough therapy in 60 years.

However, gefapixant's attractive efficacy has been limited by unwanted taste side-effects (dysgeusia, hypogeusia or ageusia). Initial human proof-of-concept study at a high dose of 600 mg twice daily led to clinically significant taste disturbances in all patients that were associated with a 25% dropout rate (Abdulqawi, 2015). Titration to lower doses led to a decrease in the taste side-effects, although these ontarget issues could not be resolved as gefapixant still led to significant taste adverse events at effective doses for cough suppression (Sheridan, 2016). The incidence of taste adverse events reported with gefapixant at the predicted therapeutic dose of 50 mg BID was 81% (Smith, 2017). The taste adverse events associated with gefapixant is believed to be due to its low selectivity for P2X3 homotrimeric receptors (involved in cough) versus P2X2/3 heterotrimeric receptors (responsible for taste perception).

Accordingly, a potent, orally bioavailable small molecule antagonist of P2X3 that is highly selective for P2X3 homotrimers versus P2X2/3 heterotrimers such as BLU-5937 would hypothetically limit unwanted taste side-effects while being efficacious in the treatment of chronic cough.

1.9. Risk/Benefit Assessment

Sponsor Project Nº CL-5937-02

1.9.1 Known Potential Risks

1.9.2. Known Potential Benefits

Chronic cough can seriously impair quality of life. The disabling effects of chronic cough are understandable, given that patients with the condition cough up to hundreds of times per hour for months to years. The treatment options of chronic cough are limited and not optimal due to either low efficacy (OTC drugs) or poor tolerance (gabapentanoids/opioids). Subjects recruited in this study may see an improvement in their symptoms. Clinical studies with another P2X3 antagonist (gefapixant) have shown significant reduction in cough frequency in chronic cough patients.

STUDY OBJECTIVES AND ENDPOINTS 2.

2.1. Primary Objective

The primary objective of this study is to assess the efficacy and safety of BLU-5937 for the treatment unexplained, refractory chronic cough.

2.2. Secondary Objective

The secondary objective is to establish the optimal therapeutic doses for the Phase 2b/3 studies.

2.3. Primary Efficacy Endpoint

Change from baseline in awake cough frequency (cough recorder) at end of each dose level.

[figure not shown]
2.4. Secondary Efficacy Endpoints

- Change from baseline in 24-hour cough frequency (cough recorder) at end of each dose level and follow up
- Change from baseline in awake cough frequency (cough recorder) at follow up

Sponsor Project Nº CL-5937-02

- Change from baseline in cough severity as measured with VAS at end of each dose level and follow up
- Change from baseline in Leicester cough questionnaire total score at end of each treatment period
- Global Rating of Change scale at end of each dose level and follow up

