8.2. General Approach

Full details of all planned analyses shall be specified in the SAP which will be finalized prior to database lock.

For continuous variables, the number of observations, mean, standard deviation, median, minimum and maximum shall be presented as appropriate. For categorical values, the number of observations and percentages shall be presented as appropriate.

Subject-level listings shall be provided to support all tabulated output.

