8.4. Efficacy Analysis

8.4.1. Primary Endpoint – Awake Cough Count

The primary efficacy endpoint is change from baseline in awake cough count by dose level derived as follows:

Change in Awake Cough Count = Post-treatment Cough Count - Baseline Cough Count

Hence a negative result indicates a decrease in cough frequency while a positive result indicates an increase.

Due to the skewed nature of cough frequency data, awake cough frequency will be log transformed prior to analysis.

The baseline scores will be recorded on Day 0 (Visit 2) and Day 30 (Visit 8) for Periods 1 and 2 respectively.

If there are any zero cough frequencies within the data all values will have 0.1 added to their cough frequency (equates to 1 cough every 10 hours) prior to transforming the data.

Sponsor Project Nº CL-5937-02

A repeated measures mixed model analysis of variance will be used to evaluate the primary endpoint. The log transformed awake cough frequency measured at assessment visits within periods will be the repeated measure.

A repeated measure mixed model (MMRM) suitable for a crossover design with repeated measures within periods will be used. The fixed effects, random effects and repeated measure structure for the model will be as follows:

Fixed effects: Sequence (AB, BA), Period (1, 2), Treatment (BLU-5937, Placebo), Assessment Visit (1 to 4 within each period) and the Treatment by Assessment Visit interaction. Average baseline (average of the 2 period baselines) and period specific baselines will be included as covariates.

Random Effects: Subject

Repeated measures structure: the model will take account of the assessment visits within subject periods

Contrast statements will be used to compare each dose of active treatment against placebo at the corresponding assessment visits of the periods. The mean change from baseline (on the log scale), with associated standard errors will be presented for each treatment at each assessment visit. Treatment differences vs placebo with corresponding 95% CIs will also be presented for each dose. Means will be back-transformed to estimate the ratio of the visit to baseline for each treatment at each visit and the treatment differences will be back-transformed to estimate the ratio of the visit to baseline for the active group, adjusted for the placebo effect. All ratios will be accompanied by their 95% CIs and the p-values comparing active doses to placebo will be presented.

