8.4.2. Secondary Endpoints

The following secondary endpoints will be analysed using the ITT analysis set.

- Change from baseline in 24-hour cough frequency at end of each dose level and follow-up
- Change from baseline in awake cough frequency at follow up

Sponsor Project Nº CL-5937-02

- Change from baseline in cough severity as measured by the Visual Analogue Scale (VAS) at end of each dose level and follow-up
- Change from baseline in Leicester cough questionnaire (LCQ) total scores at end of each treatment period
- Global rating of change scale at end of each dose level and follow-up

Statistical approaches for analysis of the secondary endpoints will be detailed in the SAP and will be generally similar in approach to that of the primary endpoint. Only cough count data will be log transformed prior to analysis.

Global rating of change scale will be remapped and given scores to create a continuous endpoint. A lower score will be considered a more positive outcome.

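### Must the plan name the baseline and contrast for the Day 60 follow-up endpoints?

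*Combined protocol and SAP*

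**What the plan says.** Section 2.4 includes "Change from baseline in awake cough frequency (cough recorder) at follow up", and Sections 2.4 and 8.4.2 set follow-up endpoints for 24-hour cough frequency and VAS in the same way. Follow-up is a single visit, nominally Day 60, after Period 2 or after early withdrawal (Section 6.6.16).

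The detailed rules stand in Section 8.4.1 and are written for the primary endpoint:

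- Baseline: "The baseline scores will be recorded on Day 0 (Visit 2) and Day 30 (Visit 8) for Periods 1 and 2 respectively".
- Covariates: "Average baseline (average of the 2 period baselines) and period specific baselines will be included as covariates".
- Contrast: "Contrast statements will be used to compare each dose of active treatment against placebo at the corresponding assessment visits of the periods", with four visits in each period.
- Reporting: "Means will be back-transformed to estimate the ratio of the visit to baseline for each treatment at each visit", together with a placebo-adjusted ratio for each dose.

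For secondary endpoints, Section 8.4.2 says the approaches "will be detailed in the SAP and will be generally similar in approach to that of the primary endpoint". It adds: "Only cough count data will be log transformed prior to analysis". Section 8.2 states: "Full details of all planned analyses shall be specified in the SAP which will be finalized prior to database lock". The file reviewed contains no SAP text on the Day 60 endpoints.

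**The concern.** The primary method does not carry over to Day 60 unaltered. There is one follow-up visit, so no corresponding visit exists under the other treatment. In a model of Day 60 alone, sequence and last treatment are the same variable, so the primary model's terms cannot simply be copied.

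The choice of baseline could also affect the answer. Where BLU-5937 came first, Day 30 is itself an off-drug reading, 10-14 days after the last dose. Where BLU-5937 came second, Day 60 is nominally the same interval after the last dose. If some effect, or a rebound, lasts that long, Day 30 is contaminated in one sequence and clean in the other. Treating it as the baseline for Day 60 would then count the residual effect twice. Persistence or rebound after stopping is exactly what an off-treatment endpoint can reveal, so the method should be sound when the effect is not zero.

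**Working it through.** **Inputs.** The Synopsis plans about 68 randomised to obtain 62 completers, and Section 5.2.3 allocates 1:1, giving 62/2 = 31 per sequence. Washout and follow-up are each 10-14 days (Section 3). Within-subject correlations and effect sizes are not in the available text, so the following are assumptions: correlation rho of 0.5 to 0.9 and compound symmetry (equal correlation between all visits). Let d be the residual effect 10-14 days after BLU-5937, equal at Day 30 and Day 60, and gone by Day 60 in the BLU-first sequence (60 - 16 = 44 days after its last dosing day). The plan states no figure for this endpoint that could be reproduced.

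**Expected difference at Day 60, BLU-last minus placebo-last.**

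1. Change from Day 30. BLU-last: d - 0 = d. Placebo-last: 0 - d = -d. Difference: d - (-d) = 2d.
2. Day 60 adjusted for Day 0 and Day 30. The Day 30 slope is rho/(1 + rho) and the sequences differ by -d at Day 30, so the estimate is d[1 + rho/(1 + rho)]: 1.33d, 1.41d and 1.47d at rho 0.5, 0.7 and 0.9.
3. Day 60 adjusted for Day 30 only: d(1 + rho), or 1.5d to 1.9d.
4. Day 60 adjusted for Day 0 only: d.
5. The primary-type joint crossover model with Day 60 as a fifth Period 2 visit: 0.99d to 1.00d under compound symmetry. It gives 1.13d to 1.37d if readings in the same period are more alike than readings across periods. If the residual effect also fades gradually through the Period 2 visits, the range is 1.17d to 1.56d.

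**On the reporting scale.** Take d as a true ratio of 0.80. Change from Day 30 gives a placebo-adjusted ratio of 0.80² = 0.64. The per-treatment ratios are 0.80 for BLU-last, which is correct, and 1/0.80 = 1.25 for placebo-last; 0.80/1.25 = 0.64. Section 8.4.1 presents both kinds of ratio, so an apparent 25% rise after placebo would appear beside the exaggerated figure. VAS is not log transformed, so there the doubling would be in millimetres.

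**Power in simulation** (31 per sequence, two-sided 5%, d = 0.3 SD):

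| Analysis | rho 0.5 | rho 0.7 | rho 0.9 |
|---|---|---|---|
| Change from Day 30 | 64% | 86% | >99% |
| Adjusted for Day 0 and Day 30 | 45% | 68% | 98% |
| Adjusted for Day 0 only | 26% | 35% | 76% |

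With d effectively zero, every version rejects about 5% of the time (4.8% to 5.8%).

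**Reading the results.** No method is best on every count. Day 0 alone is unbiased under these assumptions but has the least power. Change from Day 30 has the most power but doubles the scale. Halving it, which is the same as a paired Day 30/Day 60 comparison, estimates d with an identical test statistic. The choice therefore affects the size reported and the precision, not the validity of the test when nothing persists.

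**The case for a change.** The strongest case for a change is that the only direction given, similarity to the primary analysis, points to methods that do not fit a single follow-up visit. Section 8.4.1 names Day 30 as the later baseline, and an analyst following it literally could produce the 2d result. The remedy would be a line of SAP text using data already collected on Days 0, 30 and 60, and reasonable models spread from about 1.0d to 1.9d, or 2d for the simple change.

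The gap and the arithmetic stand. The step to a defect in the plan does not. Section 8.4.1 assigns Day 30 to Period 2, while Section 3 lists follow-up as a separate phase, so no stated rule makes Day 30 the Day 60 baseline. The exact 2d also needs equal residuals at both times, yet the washout may be extended beyond 14 days (Section 6.6.9).

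Nor is a paired Day 30/Day 60 analysis clearly the right prescription. It turns a prespecified baseline into an outcome, and it has no pair for a subject who withdraws in Period 1 and attends follow-up. Adjustment for both baselines does have less power than that paired contrast, but it has more than adjustment for Day 0 alone (45% against 26% at rho 0.5). These are choices for a SAP author to weigh.

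**Conclusion.** The concern does not call for a change to the plan. The protocol is silent on the baseline and contrast for the Day 60 awake cough, 24-hour cough and VAS endpoints, but it assigns that detail to a SAP to be completed before database lock. A competent analyst would have to settle it there, because the primary model cannot be fitted to Day 60 unaltered.

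The worst case is a doubling on the log scale (0.80 reported as 0.64). It requires three things together: a residual effect 10-14 days after stopping, which the available text does not document; its disappearance by Day 60 in the BLU-first sequence; and a simple change from Day 30 compared between sequences, which the plan does not specify. The approach nearest the primary analysis gives about 1.0d under compound symmetry and up to about 1.6d under the less favourable structures tried. With no persisting effect there is no bias and no inflation of type I error. All intermediate figures rest on assumed correlations. The primary endpoint is measured on treatment, at the end of each dose level, and is unaffected by how Day 60 is analysed.

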2.5. Exploratory Efficacy Endpoints

2.6. Safety Endpoints

- Adverse Event (AE) reporting
- Spontaneous taste disturbance AE reporting (subjects will complete a questionnaire on type, severity and duration of taste disturbance AEs)
- Vital signs
- ECG
- Clinical laboratory
- Physical exam

2.7. Pharmacokinetics

• BLU-5937 plasma levels (pre dose and 1 hour post dose)

3. STUDY DESIGN

This is a Phase 2, multicentre, randomized, double-blind, placebo-controlled, two-period crossover, dose escalation study of BLU-5937 in subjects with unexplained or refractory chronic cough.

Subjects will be screened during a period of up to 14 days and undergo a screening 24-cough monitoring using an objective measure of coughs (VitaloJAK Vitalograph, Ltd.) to exclude the mild cougher subjects (< 10 cough/hr, from awake cough count).

Approximately 68 subjects who meet entry criteria will be randomized into the study. There will be two 16-day treatment periods (BLU-5937 or placebo) with a 10-14 days washout period between treatment periods. Each Period will consist of 4 escalating dose levels. Each dose level will be of 4 days duration.

The duration of treatment for each subject is as follows:

Screening Period: up to 14 days

Sponsor Project Nº CL-5937-02

- Baseline Period 1: 1 day
- Treatment Period 1 (BLU-5937 or Placebo):
 16 days (escalating doses of 25, 50, 100, 200 mg BID or placebo; 4 days for each dose)
- Washout: 10-14 days
- Baseline Period 2: 1 day
- Treatment Period 2 (Placebo or BLU-5937):
 16 days (escalating doses of 25, 50, 100, 200 mg BID or placebo; 4 days for each dose)
- Follow-Up Period: 10-14 days

Individual subject participation is expected to be approximately 74 days including Screening, Baseline, Treatment periods and Follow-Up period.

3.1. Discussion of Study Design

This randomized, double-blind, placebo-controlled, two-period crossover, dose escalation study design has been previously used to characterize the efficacy and safety of other drugs in patients with unexplained, refractory chronic cough and was deemed acceptable by the Health Authorities in a context of early Phase 2 investigation. This particular study design will allow the testing of several doses in a restricted number of patients in view of gathering initial safety and efficacy data in the target patient population and for the selection of optimal doses to be evaluated in other clinical studies.

4. SUBJECT POPULATION

Subjects who meet all the inclusion criteria and none of the exclusion criteria at the screening visit will be eligible for participation in this study. Continued eligibility will be assessed upon admission to the clinical site at Visit 3 (Day1), prior to the first study drug administration.

Screen failures are defined as participants who consent to participate in the clinical trial but are not subsequently randomly assigned to the study intervention or entered in the study.

4.1. Inclusion Criteria

[figure not shown]
Subjects who meet all of the following criteria will be included in the study:

- 1. Have provided written consent and are willing and able to comply with all aspects of the protocol.
- 2. Women and Men between 18 and 80 years of age inclusive.
- 3. Chest radiograph or CT thorax within the last 5 years from screening not demonstrating any abnormality considered to be significantly contributing to the chronic cough in the opinion of the Principal Investigator and Medical Monitor.
- 4. Have unexplained, refractory chronic cough for at least one year: a cough that is unresponsive to at least 8 weeks of targeted treatment for identified underlying triggers including reflux disease, asthma and post-nasal drip or unexplained cough; or a cough for which no objective evidence of an underlying trigger can be determined after investigation (see Appendix 1).
- 5. Awake Cough Count of ≥ 10 per hour (Cough Count at Screening).
- 6. A score of \geq 40mm on the Cough Severity VAS at Screening.
- 7. Women of child-bearing potential must have a negative serum pregnancy test at Screening.

Sponsor Project Nº CL-5937-02

- 8. Women of child-bearing potential must use a highly effective contraception method from Screening through the Follow-Up Visit. Acceptable birth control methods include:
 - a. intrauterine device (IUD) or intrauterine system (IUS);
 - b. tubal ligation; or male sterilization.
 - c. When in line with the preferred life style of the subject, true and complete abstinence (not periodic abstinence) is acceptable.

For the purposes of this study, a female of childbearing potential is defined as any female who has experienced menarche and is pre-menopausal; a postmenopausal state is defined as no menses for 12 months without an alternative medical cause in a previously menstruating female.

4.2. Exclusion Criteria

Subjects are NOT eligible for this study if they meet any of the following criteria:

- Current smoker or vaper.
- 2. Individuals who have given up smoking or vaping within the past 6 months, or those with >20 pack-year smoking history.
- 3. Diagnosis of COPD, bronchiectasis, idiopathic pulmonary fibrosis based on clinician assessment.
- 4. Criteria No.4 removed from here in protocol v5.0. See Table 2 section 4.4 for details.
- 5. FEV1/FVC < 60%.
- 6. History of upper respiratory tract infection or recent significant change in pulmonary status within 4 weeks of the Baseline/Visit 2 (Day 0).
- 7. Criteria No.7 removed from here in protocol v5.0. See Table 2 section 4.4 for details.
- Requiring concomitant therapy with prohibited medications or non-pharmacological therapy (see Table 2, Section 4.4).
- Medical history of hypogeusia/dysgeusia or known presence of a dysfunction in his/her ability to taste.
- 10. History of concurrent malignancy or recurrence of malignancy within 2 years prior to Screening (not including subjects with <3 excised basal cell carcinomas).
- 11. History of a diagnosis of drug or alcohol dependency or abuse within the last 3 years.
- 12. Any condition possibly affecting drug absorption (e.g., gastrectomy, gastroplasty, any type of bariatric surgery, vagotomy, or bowel resection).
- 13. Screening systolic blood pressure (SBP) >160 mm Hg or a diastolic blood pressure (DBP) >100 mm Hg.
- 14. Clinically significant abnormal electrocardiogram (ECG) at Screening, including any of the following:

Sponsor Project Nº CL-5937-02

- a. OTcF interval >450 milliseconds
- b. Atrial fibrillation or atrial flutter
- c. Heart rate <40 beats per minute >110 bpm
- d. Second degree or third degree (complete) AV block
- e. Left bundle branch block (including hemiblock)
- f. Wolf-Parkinson-White Syndrome
- g. Personal or family history of congenital long QT syndrome or family history of sudden death
- 15. Clinically significant abnormal laboratory tests at Screening, including:
 - a. Alkaline phosphatase (ALP), alanine aminotransferase (ALT, SGPT), aspartate aminotransferase (AST, SGOT) >150% of the upper limit of normal (ULN), gamma-glutamyl transferase (GGT) >200% of the upper limit of normal (ULN), or Total bilirubin above the upper limit of normal (ULN)
 - b. Creatinine >200% of the upper limit of normal (ULN)
 - c. Unexplained creatine kinase concentration >3 x ULN
 - d. haemoglobin < 10 g/dL, WBC count <2500 mm3, neutrophil count <1500 mm3, platelet count <100 × 103/mm3
 - e. Positive tests for drugs of abuse (certain drugs of abuse are acceptable for non-cough indications see section 4.4)
- 16. Significant coagulopathy as defined by a known hereditary deficiency of coagulation factors or platelet function or an unexplained elevation of the prothrombin time (PT) or international normalized ratio (INR) of >1.5.
- 17. Criteria No.17 removed from here in protocol v5.0. See 15c above for details.
- 18. Breastfeeding.
- 19. Criteria No.19 removed from here in protocol v5.0. See Table 2 section 4.4 for details.
- 20. Blood donation within 56 days or plasma donation within 7 days prior to dosing.
- 21. Other severe, acute, or chronic medical or psychiatric condition or laboratory abnormality that may increase the risk associated with trial participation or investigational product administration or may interfere with the interpretation of trial results and, in the judgment of the Investigator or Sponsor, would make the subject inappropriate for entry into this trial.

